3.5.2. Anticipated Adverse Events (AEs) Associated with the TPS Placement, Residence, and Removal

Anticipated AEs associated with the TPS placement and removal procedures and TPS residence may include, but are not limited to, the following:

- Abdominal cramps and discomfort from the air used to distend the stomach
- Aspiration of gastric contents, aspiration pneumonia
- Complications related to sedation and anesthesia
- Complications related to upper GI endoscopy and the use of routine endoscopic instruments
- Infection in the throat, esophagus, stomach, or duodenum
- Gastric, esophageal, or pharyngeal trauma, including sore or irritated throat, ulceration, bleeding, or perforation in upper GI tract, and their associated complications

- Injury to the digestive tract by the TPS delivery system or during device removal
- TPS placement in an improper location such as in the esophagus or duodenum, which results in obstruction, bleeding, or perforation
- Esophageal sphincter and/or pyloric sphincter incompetency associated with sphincter dilation during placement, residence or removal of the TPS
- Inability to endoscopically remove part or all of the TPS device, which may result in the need for surgery
- Cardiac or respiratory arrest during endoscopy
- Halitosis
- A feeling of heaviness in the abdomen
- Abdominal or back pain, either steady or cyclic
- Gastric discomfort, feelings of nausea, and vomiting
- Constipation or diarrhea
- Dyspepsia
- Allergic reaction to the device's materials (e.g., silicone, barium sulfate and parylene)
- Excess reduction in oral intake, resulting in dehydration or malnutrition
- Alteration of the absorption rate of medications, particularly to enteric-coated medications
- Influence on medication dosing, leading to the need to adjust dosing and potential associated complications if dosing is not adjusted, such as hypoglycemia, hypotension, etc.
- Influence on digestion of food
- Pharyngeal, esophageal, or gastrointestinal obstruction by the TPS
- Formation of intragastric bezoars
- Gastroesophageal reflux
- Distension of stomach
- Injury or irritation to upper GI tract, resulting in acute or chronic tissue inflammatory response, pain, bleeding, erosion, ulceration, strictures, stenosis, or perforation
- Bacterial or fungal growth on the surfaces of the TPS, resulting in infection
- Biliopancreatic infection or obstruction, cholecystitis, pancreatitis
- Need for medication, endoscopic intervention, early TPS removal, or surgery to treat/correct complications
- Death

3.5.3. Residual Risks Associated with the Investigational Device, as Identified in the Risk Analysis Report

BAROnova has conducted extensive assessment of the risk associated with the device. The conclusion of the current risk assessment is that, with respect to perceivable conditions in which the product would be subjected to a worst-case environment or human error scenario, the outcome of the residual risk is considered acceptable as none of the recognized hazards leads to a risk within the intolerable range.

The risk assessment does not contain foreseeable risks of intolerable levels. The device is designed and manufactured such that, when used as intended, it will not compromise the conditions of safety of the patients or operator, and any remaining risk is managed with a high level of protection of subject safety.

3.5.4. Risks Associated with Participation in the Clinical Investigation

There are risks associated with participation in a clinical investigation. There is only limited clinical experience with the device to date and there may be unanticipated adverse events. There are protocol-defined tests and follow-up studies such as endoscopy that may carry additional risk to the subjects. In addition, this is a sham-controlled, double-blinded study. The sham procedure and the blinding may carry additional risk to the subjects.

3.5.5. Possible Interactions with Concomitant Medication

The effect of the TPS device to the absorption of orally administered medication is unknown. The physician should evaluate the risk and benefit of this procedure for patients who take concomitant medications and carefully monitor the patients.

Patients who receive hypoglycemic or anti-hypertension agents should be monitored closely as their medication dosages may need to be adjusted with the decrease in food intake and weight loss.

3.5.6. Minimization of Risks

The following steps have been taken to further minimize the risks of the study:

- The study protocol has built in measures to control potential adverse effects, including study inclusion/exclusion criteria, prophylactic medications, clinical and endoscopic surveillance, guidelines for post-procedure management, and provisions for early removal of the device if necessary.
- Patient informed consent contains sufficient information on the potential risks.
- Subjects will be provided with subject information cards that contain brief device and physician contact information if needed
- Unblinding is permitted when the Investigational Device information is necessary for the management of adverse events and ensuring subject's safety
- Training and technical support will be provided for device placement/removal procedures in the study
- A DSMB is set up to monitor the safety of the study

In summary, subjects included in the present study have a clinical indication for weight loss. Prior clinical experience shows that the device can be deployed successfully, that subjects achieve significant weight loss over a 3-6 month residence time, and that the complications can be managed clinically. The risks associated with the device have been mitigated to the extent possible. The current study design includes additional measures to further minimize risks. These data and study design features indicate a favorable risk-benefit profile for the subjects to be included in the present study.

4. STUDY OBJECTIVES

The objective of this study is to demonstrate the safety and effectiveness of the BAROnova TransPyloric Shuttle for weight reduction in patients with BMIs of 30-40 kg/m² compared with the sham-control over the 12 months treatment period.

The study will also assess, as secondary endpoints, changes in weight-related comorbidities, weight-related quality of life, and eating behavior.

The study will be considered a success for efficacy purposes if it meets both of the primary efficacy analyses.

The safety will be characterized, with all adverse events reported. The Clinical Event Committee (CEC) will adjudicate all serious device-related adverse events and any other events deemed necessary.

5. STUDY DESIGN

5.1. Study Design

This is a multicenter, prospective, randomized, parallel design, double-blinded, sham-controlled study. A total of 270 subjects are planned for the pivotal study cohort. Subjects meeting the general inclusion/exclusion criteria will undergo baseline endoscopic assessment. Those who meet endoscopic eligibility will be randomized in a 2:1 allocation to the Treatment or Control group stratified according to center. The Treatment group will receive the TPS placement and the Control group will receive a sham endoscopic procedure that does not include TPS placement.

Subjects will be followed up for 12 months after the index procedure or until the device is removed.

[figure not shown]
At 12 months, subjects in the Treatment group will undergo an endoscopic assessment followed by the TPS removal. Subjects in the Control group will complete all the same assessments as the Treatment group except the endoscopy.

Subjects who achieve a BMI of ≤ 22 kg/m² for two consecutive visits before the 12-months follow up will be considered a treatment success, have the device removed if in the Treatment group, and exit the study. A BMI of 22 kg/m² is selected as a reference value since it is a midpoint value of the normal BMI range, and a BMI ≥ 23 kg/m² has been shown to be associated with an increased risk of developing diabetes in the Nurses' Health Study that followed 43,581 women over 8 years.²⁸ The handling of these subjects in the analysis is described in Section 15.5.

Subjects in both groups will receive the same lifestyle modification education and counseling during the 12-month follow up duration. In brief, subjects will receive written instruction in lifestyle modification strategies for weight loss (e.g., caloric restriction, increasing physical activity, behavioral modification, etc.) at the beginning of the study. At each follow up visit, subjects will receive a brief (15 minute) lifestyle modification counseling performed by a medical provider (i.e., registered dietitian, nurse, behavioral health specialist)

trained in the delivery of the intervention. In months 7, 8, 10, and 11 where an in-person follow-up visit is not scheduled, site provider will have a brief (15 minute) telephone call with the subject. During these calls, the provider and patient will discuss changes in weight, diet, eating behavior and physical activity over the past month. These calls are designed to promote adherence to the lifestyle modification strategies previously taught to the subject.

A schematic diagram of the study design is shown in Figure 12.

*telephone contacts at 7, 8, 10, 11M

Figure 12. Study Diagram

5.2. Subject Recruitment and Enrollment

Subjects will be recruited by Investigators at each study site. Candidates may be recruited during routine office visits; by IRB-approved advertisements such as brochures, flyers, letters, and other methods in the individual sites; or by referral from IRB-approved sponsor's advertisements in newspapers, radio, the internet, or other methods. Candidates who are potentially eligible for the study will be scheduled for a screening visit.

After giving written informed consent, subjects will undergo screening assessments. As part of the recruitment and enrollment process, potential participants will undergo a behavioral/psychosocial evaluation similar to that performed prior to bariatric surgery, as recommended by the American Society for Metabolic and Bariatric Surgery, and required by most third party payers for reimbursement for bariatric surgery.²⁹ This clinical assessment will include direct questioning about the potential participants psychosocial status (with specific focus on symptoms of disordered eating and depression), mental health treatment history, and a review of the potential participant's current diet and regular eating behaviors. This evaluation is designed to assess for the presence of significant psychopathology that would contraindicate weight loss treatment and/or successful participation in the study. The evaluation will be performed by a member of the study team (registered dietitian, behavioral specialist, mental health professional, etc.) who will be trained by a consultant to the study with extensive expertise in the psychosocial and behavioral aspects of obesity and bariatric surgery. This consultant also will provide periodic supervision to the individuals performing these evaluations and to ensure that the sites are using similar criteria to evaluate and include/exclude study participants.

Screening data will be reviewed to determine subject eligibility. Subjects who meet all inclusion criteria and none of the general exclusion criteria will be scheduled for a baseline visit within one week of the planned procedure. Subjects who remain eligible after the baseline visit will be scheduled for the procedure.

On the day of the procedure, subjects will undergo endoscopic assessment to confirm endoscopic eligibility. Subjects who meet the endoscopic exclusion criteria will be excluded from the study and will be considered a screening failure. Subjects who meet the endoscopic eligibility will be randomized using a web-based randomization tool provided by the study data management organization. A TPSS Access Sheath is placed allowing delivery of the TPS during the same procedure. TPS is delivered in the treatment group but not in the control group.

A subject is considered enrolled in the study when the subject has given written informed consent and the TPSS Access Sheath has been placed in the subject.

5.3. Randomization and Masking

Eligible subjects will be randomized to either the Treatment or the Control group in a 2:1 ratio stratified according to center. Randomization will be according to a random permuted block design within strata. Block size of 3 and 6 will be used.

Randomization occurs on the day of the procedure after endoscopic screening. The Investigator who performs the index procedure and endoscopic follow-ups will not collect the primary outcome data. The Investigator and/or the study coordinator who collect the primary outcome data will be masked to the subject's intervention.

The subject will be blinded to the intervention for the duration of participation in the study.

The Clinical Event Committee (CEC) will be masked to the subject’s intervention. The Data Safety Monitoring Board (DSMB) will have access to unmasked subject data, as required, to monitor and evaluate the safety data throughout the study.

5.4. [REDACTED]

[REDACTED]

[REDACTED]

[REDACTED]

[REDACTED]

[REDACTED]

5.5. [REDACTED]

[REDACTED]

[REDACTED]

[REDACTED]

[REDACTED]

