45. The Investigator judges the candidate unsuitable for the study

46. Have any of the following endoscopic exclusion criteria:

- a. Esophageal stricture
- b. Barrett's esophagus
- c. Erosive esophagitis
- d. Varices
- e. Angiectasias
- f. Gastric mass
- g. Antral or peri-pyloric polyps
- h. Peptic ulceration
- i. Hiatal hernia ≥ 4 cm
- j. Pyloric stricture
- k. Any other abnormalities or characteristics that preclude safe use of the TPS

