11.9.3. Index Procedure (Day 0)

The TPS placement procedure will be performed under general or monitored anesthesia care (MAC). Eligible subjects will undergo standard preparation for an endoscopic procedure, followed by an endoscopic assessment of the esophagus, stomach, antrum, pylorus and duodenum. Subjects who meet the endoscopic exclusion criteria will be considered an endoscopic screening failure and excluded from the study.

Subjects who do not possess any endoscopic exclusion criteria will be randomized into Treatment or Control group using a web-based randomization system provided by the study data management organization. Procedure details can be found in the instruction for use (IFU). In brief, a TPSS Access Sheath is inserted over the gastroscope using standard techniques to position the distal tip approximately 6 cm below the gastroesophageal junction. Endoscopic visualization is used to monitor inflation of the distal positioning balloon on the Access Sheath and confirm final insertion position. After removal of the gastroscope and obturator, the TPS Delivery Device is lubricated and inserted into the Access Sheath until fully-seated with the connectors engaged. The TPS Delivery Device is placed on the TPSS Stand and connected to the insufflation system. Deployment of the TPS is accomplished by forward rotation of TPS Advance Torque Knob on the delivery device handle. Following actuation of the TPS locking mechanisms on the TPS Delivery Device, the formed TPS is released into the stomach and the Access Sheath and TPS Delivery Device are withdrawn from the patient. A final endoscopic evaluation is performed to inspect the final device configuration and assess the gastroesophageal tissues prior to completion of the procedure.

In the Control subject, the sham procedure consists of anesthesia and the TPSS Access Sheath placement but no TPS delivery. Effort will be made so that the overall sham procedure time is similar to the TPS placement procedure time.

Subject will be discharged when the site and physician's discharge criteria are met (if designated by the hospital policy and procedures).

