16.6. Maintain Blinding during the Study

Only the data management organization and the unblinded statistician have access to the randomization code. The Sponsor's study management team, the Study Steering Committee, the CEC, and the statistician who is responsible for study design and data analysis will be blinded to subject's treatment during the study. The monitors from the monitoring organization will have access to subjects' treatment information in order to perform study monitoring and source data verification.

At each site, the Investigator who performs the index procedure and endoscopic follow up will not collect the outcome data. The Investigator or study coordinator who collects outcome data will be masked. Source documents containing subject treatment information will be either masked or access-controlled according to each site's practice. Each site's blinding procedure will be assessed by the study monitors at the monitoring visits.

In exceptional circumstances when knowledge of the Investigational Device is essential for patient safety in case of serious adverse event, the blinding for this subject may be broken.

The Investigator should promptly (within 24 hours) document and explain to the Sponsor any premature unblinding (e.g., accidental unblinding, unblinding due to a serious adverse event) of the study subject.

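### Section 5.3 prints the block sizes (3 and 6) in the protocol that sites hold, so an operator who tracks a centre's allocations could be certain of about 9% of assignments; withholding the sizes is a free, minor improvement

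*Combined protocol and SAP*

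**What the plan says.** Section 5.3 sets out the scheme: "Eligible subjects will be randomized to either the Treatment or the Control group in a 2:1 ratio stratified according to center". It continues: "Randomization will be according to a random permuted block design within strata", and then "Block size of 3 and 6 will be used". It does not say how the two sizes are mixed or ordered.

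On timing, the same section says "Randomization occurs on the day of the procedure after endoscopic screening", and Section 11.9.3 agrees: "Subjects who do not possess any endoscopic exclusion criteria will be randomized into Treatment or Control group". The endoscopic exclusions in Section 7.3 end with an open item, 46k: "Any other abnormalities or characteristics that preclude safe use of the TPS".

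On masking, Section 5.3 says "The Investigator who performs the index procedure and endoscopic follow-ups will not collect the primary outcome data". That person places the device or performs the sham, so the allocation is known to them once the procedure is done.

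The safeguards are a web-based randomisation tool (Sections 5.2 and 11.9.3) and restricted access to the list (Section 16.6): "Only the data management organization and the unblinded statistician have access to the randomization code". Section 16.1 has all Investigators trained on the protocol before they enrol anyone. No visible section keeps the block sizes from sites or gives the endoscopic eligibility decision to someone unaware of the site's past allocations.

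**The concern.** Restricting the list conceals the next assignment only if it cannot be inferred. With blocking within centre, published block sizes and an operator who has seen earlier allocations, some assignments follow by logic. Section 11.9.3 describes endoscopic assessment, randomisation and placement as one session, so the person with that knowledge may also be deciding whether the next candidate passes a discretionary criterion.

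At stake is selective entry to the arms. Masked weighing protects the measurement of weight, not the composition of the groups. A candidate screened out under 46k is never randomised, so no analysis set defined in Section 15.2 can recover that person. Section 5.7 claims that the design minimizes bias in patient selection, and the printed sizes weaken that claim slightly for no evident gain: sites randomise through a web tool and do not need them.

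**Working it through.** **Inputs.** 2:1 by centre, blocks of 3 and 6 (Section 5.3); 270 subjects from up to 12 sites, no site above 25% (Section 7.1). Average site: 270/12 = 22.5. Largest: 0.25 × 270 = 67.5. Assumptions not in the documents: the observer has seen every earlier allocation at the site, updates exactly by Bayes' rule, and each block is 3 or 6 with equal chance.

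**The plan's own figures.** The plan gives none for predictability. The nearest figure that uses the 2:1 split is the 90% power in Section 15.4. The standard error is 9 × √(1/162 + 1/81) = 1.225. Then (8 − 4)/1.225 − 1.96 = 1.31, and Φ(1.31) = 90.4% (90.2% by noncentral t). It reproduces, and this point does not affect it.

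**How certainty arises.** Two Controls at the start of a site cannot occur in a block of 3, so the block is 6 and the next four are all Treatment. Four Treatments at the start likewise mean a block of 6, with two Controls to follow. Each opening has probability 1/2 × 1/15 = 1/30.

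**Sizes known, current block unknown (simulation, 4,000 sites per setting).**

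| Subjects per site | Mix of 3 : 6 | Certain | Certain Treatment | Certain Control | Best guess right | Sites with at least one certain |
|---|---|---|---|---|---|---|
| 22 | 1:1 | 9.5% | 7.5% | 1.9% | 75% | 66% |
| 22 | 2:1 | 7.0% | 5.5% | 1.5% | 75% | 54% |
| 22 | 1:2 | 11.5% | 9.2% | 2.3% | 74% | 74% |
| 10 | 1:1 | 8.2% | 6.7% | 1.5% | 74% | 36% |
| 67 | 1:1 | 10.1% | 8.0% | 2.1% | 75% | 97% |

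Repeat runs at 22 per site with equal mixing gave 9.2% and 9.3%. Over 270 subjects, 0.094 × 270 ≈ 25 assignments are certain, of which about 0.019 × 270 ≈ 5 are Control. Always guessing Treatment is right 67% of the time.

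**Sizes withheld (true blocks still 3 and 6, 22 per site).** The observer now spreads belief over several possible schemes, some with blocks of 9 or 12. Strict certainty falls from 9% to 0%. Best-guess accuracy stays at 75%. Assignments at least 80% likely to be Treatment stay at about 34%. Assignments called with more than 95% probability fall from 9% to between 1% and 5%, depending on the assumed schemes. I obtained about 1% with four mixed schemes (3/6, 6/9, 3/6/9, 6/9/12) and about 5% with seven (the same four plus single sizes 3, 6 and 9), equally weighted in each case.

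**If block boundaries and size were known.** The expected certain run at the end of a block with T Treatments and C Controls is T/(C+1) + C/(T+1). Size 3: (1 + 1/3)/3 = 44%. Size 6: (4/3 + 2/5)/6 = 29%. Section 5.3 does not disclose boundaries, so these are not the effect of the printed sentence.

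**The case against.** The strongest reply is that deletion buys little. Accuracy of 75% against 67% comes from small blocks, 2:1 allocation and visible past allocations, and withholding the sizes does not change it. This stands: that comparison must not be used as the harm from disclosure. What deletion removes is certainty. Even that assumes the observer does not simply guess 3 and 6, the two smallest block sizes possible at 2:1.

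Second, a reader might infer that the operator at each site knows every earlier allocation. The documents do not say how many operators a site has, and Sections 16.1 and 16.2.1 speak of Investigators in the plural. With several operators, or imperfect recall, the certain share is smaller. This stands, and makes 9% the figure for a best-informed observer.

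Third, a reader might infer that selection will bias the weight-loss comparison. Nothing shows that. Candidates have passed screening, behavioral evaluation and a baseline assessment by then; 46k asks about safe use of the device, not expected weight loss; and most certain assignments are Treatment, already the two-in-three default. The web tool, the mixing of sizes, the masked outcome collectors and the baseline comparison in Section 15.5.2 also help. None of them, however, prevents inference from known sizes and past allocations.

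**Conclusion.** The point holds as a minor weakness in allocation concealment. Publishing the sizes lets a well-informed operator be certain of about 9% of assignments (7% to 11.5% across mixes; about 7% Treatment and 2% Control). This assumes one operator doing most procedures at a site of about 22 subjects, with full recall. Withholding the sizes takes strict certainty to zero for an observer who allows for larger blocks, and leaves best-guess accuracy at about 75%.

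A reader might go further and conclude that blocks of 3 and 6 are wrong, or that the sizes must be changed during the trial. The documents do not support that. Small blocks keep the arms balanced within up to 12 centres, which is a legitimate choice. The defect is the disclosure, for which the documents show no benefit.

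**What to change.** In Section 5.3, replace the sentence giving the sizes with wording such as: *random permuted blocks of varying size; sizes are held by the data management organization and not disclosed to sites*. Keep the actual sizes and the rule for mixing them in a restricted randomisation specification, under the access limits of Section 16.6.

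This changes one sentence and adds a controlled document. It costs nothing in within-centre balance, power or conduct. It cannot undo knowledge at sites that already hold the current text.

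Larger blocks are a separate, optional trade-off. With sizes 6, 9 and 12, even if known, about 2% of assignments are certain and the best guess is right 71% of the time, at the price of looser balance within centres. Changing sizes after randomisation has begun alters the scheme mid-trial and is more than a wording change. Neither is needed to resolve this point.
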